Protocol Title: An Open Label, Randomized Phase 2 Trial of Pomalidomide/Dexamethasone With or Without Elotuzumab in relapsed and refractory Multiple Myeloma

Investigational Product(s), Dose and Mode of Administration, Duration of Treatment with Investigational Product(s):

See **Study Schema** for details

Control Arm

Pomalidomide: 4 mg PO QD Days 1-21 of each cycle

Dexamethasone:

- Subjects \leq 75 years old: 40 mg PO Days (1, 8, 15 and 22) of each cycle
- Subjects $>$ 75 years old: 20 mg PO Days (1, 8, 15 and 22) of each cycle

Elotuzumab Arm

Elotuzumab:

- Cycle 1 - 2: 10 mg/kg IV Days 1, 8, 15 and 22 of each cycle
- Cycle 3 and beyond: 20mg/kg IV Day 1 of each cycle

Pomalidomide: 4 mg PO QD Days 1-21 of each cycle

Dexamethasone: Days 1, 8, 15 and 22 of each cycle

- Subjects \leq 75 years old: weeks with elotuzumab dosing: 28 mg PO + 8 mg IV and 40 mg PO on non-elotuzumab dosing weeks
- Subjects $>$ 75 years old: weeks with elotuzumab dosing: 8 mg PO + 8 mg IV and 20 mg PO on non-elotuzumab dosing weeks

A cycle is defined as 28 days. Treatment with study drug continues until disease progression, unacceptable toxicity (adverse event related to study drug), or subject meets other criteria for discontinuation of study drug outlined in [Section 3.5](#).

Study Phase: 2

[figure not shown]
Primary Objective:

- To compare progression free survival (PFS) between treatment arms

Secondary Objectives:

- To compare objective response rate between treatment arms
- To compare overall survival between treatment arms

Study Schema

Study Population:

Subjects who are diagnosed with relapsed and refractory multiple myeloma defined as:

- 1) Must have received ≥ 2 prior lines of therapy (See [Appendix 1](#)) which must have included at least 2 consecutive cycles of lenalidomide and a proteasome inhibitor alone or in combination.
- 2) Documented refractory or relapsed and refractory (R/R) multiple myeloma
- 3) Refractory (progressed on or within 60 days of treatment) to their last treatment.
- 4) Subjects must have failed treatment with a proteasome inhibitor and lenalidomide in one of the following ways.
 - a) “Refractory” to proteasome inhibitor and lenalidomide, and to their last treatment.
 - b) “Relapsed and refractory”= patients had achieved at least a partial response to previous treatment with proteasome inhibitor or lenalidomide, or both, but progressed within 6 months, and were refractory to their last treatment

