4.5.3 Dose Delay, Interruption, or Discontinuation, All Subjects

If the dose of one drug in the regimen (ie, pomalidomide, dexamethasone, or elotuzumab) is delayed, interrupted, or discontinued, the treatment with the other drugs may continue as scheduled. However, if dexamethasone is delayed or discontinued discuss ongoing elotuzumab administration with the medical monitor. Also see [Section 3.5](#) for delays in study drugs.

Each cycle is 28 days. While dose delays or interruptions are permitted, the start of each cycle cannot be delayed and is fixed (ie, anchored) relative to Cycle 1 Day 1. Adjustments to the Cycle 1 Day 1 anchored schedule should not be performed. Should the start of a cycle be delayed, it is expected the following cycle begin as anchored to Cycle 1 Day 1. For example, if a subject is unable to start Cycle (X) until 3 days after the anchored start date, all assessments should be recorded on Cycle (X) Day 3. The following cycle should begin on Day 1 (not Day 3) of Cycle (X+1). Missed doses should be skipped, not delayed, if not given within the allowed window.

Subjects may continue on study therapy even if components of the study therapy must be discontinued. For example, a subject on pomalidomide and dexamethasone may continue on study therapy even if dexamethasone must be discontinued for an adverse event. Likewise, a subject on the elotuzumab arm may continue on study therapy if elotuzumab must be discontinued for an adverse event or other reason. Subjects are considered still on study therapy even if they continue solely on pomalidomide or dexamethasone.

Please consult the BMS Medical Monitor or any questions regarding dose interruption or study

Subjects should be instructed that if a dose of pomalidomide has been missed and it has been less than 12 hours since the subject’s regular dosing time, to take pomalidomide as soon as the subject remembers. If it has been more than 12 hours, the dose must be skipped. Subjects should not take 2 doses at the same time

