7.4.2.2 Elotuzumab Dose Delay

A delay for elotuzumab will be computed based on records from the dosing CRF page. A delay in elotuzumab dosing will be defined as the number of days from the start date of the previous infusion to the start date of the current infusion being > 8 days and ≤10 days (if in cycles 1, 2 or cycle 3) or > 29 days and ≤ 35 days (from cycle 3 - onwards).

For courses with a delay of elotuzumab infusion, the time of delay in infusion will be summarized in the categories: 2-3 days, 4-7 days.

The number and percentage of subjects with any dose delay, with 1, 2, 3, or ≥ 4 reported delays will be summarized. For subjects with a delay, their reason for delay (from the dose modification page of the CRF) will be summarized in the groups: “hematologic toxicity”, “non-hematologic toxicity”, “AE”, “dosing error” and “other”. For subjects without an available reason for delay, the category “unknown” will be used.

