7.4.2.3 Elotuzumab Dose Omission

An omission for elotuzumab will be calculated based on records from the dosing CRF page. If the interval between the two dosing dates for elotuzumab is > 10 days (in cycles 1, 2 or cycle 3) or > 35 days (from cycle 3 onwards), the dose will be considered to have been omitted.

For courses with an omission of elotuzumab infusion, the time between the previous and current infusion will be summarized in the categories: < 11 - 14, 15 - 21, 22-35, > 35 days.

The number and percentage of subjects with a dose omission, and with 1, 2, 3, or ≥ 4 omissions will be summarized. For subjects with an omission, their reason for omission (from the dose modification page of the CRF) will be summarized in the groups: “hematologic toxicity”, “non-hematologic toxicity”, “AE”, “dosing error” and “other”. For subjects without an available reason for omission, the category “unknown” will be used.

A by-subject listing for dose delay and omission will be presented for all treated subjects. This listing will include all reported delays or omission per CRF, regardless of whether the subject had a computed delay or omission based on the actual dosing dates.

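### Elotuzumab delays and omissions are counted from gaps between infusions, not against the schedule anchored to Cycle 1 Day 1, so the per-subject 1/2/3/≥4 counts are misclassified

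*SAP*

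**What the plan says.** **Protocol.** The synopsis gives the elotuzumab schedule as "Cycle 1 - 2: 10 mg/kg IV Days 1, 8, 15 and 22 of each cycle" and then "Cycle 3 and beyond: 20mg/kg IV Day 1 of each cycle". Section 4.5.3 says that "the start of each cycle cannot be delayed and is fixed (ie, anchored) relative to Cycle 1 Day 1", and adds: "Missed doses should be skipped, not delayed, if not given within the allowed window". Adding the protocol day numbers to the fixed cycle starts gives every planned infusion a known calendar date.

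**SAP.** Section 7.4.2.2 defines a delay from "the number of days from the start date of the previous infusion to the start date of the current infusion". The gap must be more than 8 and at most 10 days in Cycles 1, 2 or 3, or more than 29 and at most 35 days from Cycle 3 onwards. Section 7.4.2.3 uses the interval between two dosing dates. Above 10 or 35 days respectively, "the dose will be considered to have been omitted" (one dose, whatever the length of the gap). Both sections then tabulate subjects with 1, 2, 3 or ≥4 events. Section 8.7 lists both summaries among the topline outputs.

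**The concern.** The protocol's schedule does not shift when a dose is late or missed, but the SAP measures each infusion from the one before it, as if it did. The two agree for most isolated events. They part company when several doses in a row are missed or late, when a dose is given early, and where weekly dosing changes to four-weekly dosing.

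At stake is an accurate account of how the only investigational product was delivered. Protocol 3.5 allows treatment to be held for up to 84 days for reasons unrelated to study therapy, so gaps that span several doses are foreseen. In addition, SAP 7.4.2.8 summarises omissions of IV dexamethasone, the elotuzumab premedication, as reported. The two omission tables could therefore disagree for the same visits.

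**Working it through.** **Inputs.** The planned study day for cycle c, day d is (c − 1) × 28 + d. Weekly phase (Protocol synopsis): days 1, 8, 15, 22, 29, 36, 43, 50. Four-weekly phase: days 57, 85, 113, 141 and so on. The gap limits are those of SAP 7.4.2.2 and 7.4.2.3.

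**The SAP's own figures.** Days of delay = gap − nominal interval.
- Weekly: 9 to 10 minus 7 gives 2 to 3 days.
- Four-weekly: 30 to 35 minus 28 gives 2 to 7 days.

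These match the SAP's delay categories of 2-3 and 4-7 days, so the limits have been read as intended.

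**Conventions for the comparison.** A dose counts as late if given 2 or more days after its planned date, the smallest delay in the SAP's categories. The limit applied is the one for the cycle of the current infusion. The SAP does not spell this out, and it names Cycle 3 under both limits. Naming Cycle 3 under the weekly limit makes sense only on this reading, because an on-time Cycle 4 Day 1 dose would otherwise breach that limit.

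**Skipped doses**

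| Skipped | Infusion days either side | Gap (days) | SAP count | Count by planned date |
|---|---|---|---|---|
| C1D8 | 1, 15 | 14 | 1 omission | 1 omission |
| C1D8, D15 | 1, 22 | 21 | 1 omission | 2 omissions |
| C1D8, D15, D22 | 1, 29 | 28 | 1 omission | 3 omissions |
| C1D15 to C2D8 | 8, 43 | 35 | 1 omission | 4 omissions |
| C3D1 | 50, 85 | 35 | 1 delay, 0 omissions | 1 omission |
| C4D1, C5D1 | 57, 141 | 84 | 1 omission | 2 omissions |

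In general, a run of k skipped doses followed by an infusion counts as 1, so k − 1 are lost. The skipped C3D1 is the exception: its 35-day gap is just inside the four-weekly delay limit, so a dose that was never given appears as a 7-day delay of the next one.

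**Late or early doses**

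| History | Infusion days | Gaps (days) | SAP count | Count by planned date |
|---|---|---|---|---|
| C1D8, D15, D22 each 2 days late | 1, 10, 17, 24 | 9, 7, 7 | 1 delay | 3 delays |
| C1D8, D15, D22 late by 1, 2, 3 days | 1, 9, 17, 25 | 8, 8, 8 | 0 delays | 2 delays |
| C4, C5, C6 Day 1 each 5 days late | 57, 90, 118, 146 | 33, 28, 28 | 1 delay | 3 delays |
| C1D8 given on day 6, D15 on time | 1, 6, 15 | 5, 9 | 1 delay | 0 delays |
| C4D1 given 9 days late | 57, 94 | 37 | 1 omission | 1 late dose, if the visit window allows it |

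The last two rows err upwards. The delay counts in this table apply only if the SAP tabulates computed delays.

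**Illustration of size.** The documents give no skip rates, so these are assumptions. With 8 weekly and 4 four-weekly doses and independent skips at 5%, 10%, 20% or 30% per dose, simulation has the gap rule capturing about 78%, 75%, 67% or 59% of omitted doses. If a skip is followed by another with probability 0.5 or 0.7, it captures about 43% or 26%. These figures count skips after the last infusion as omissions. If those are treated as discontinuation, the shortfall is smaller.

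**The case against.** The strongest reply is that other outputs already carry much of the information.

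- **Gap bands.** SAP 7.4.2.3 bands the gap behind each omission (up to 14, 15-21, 22-35 and >35 days). With on-schedule resumption in the weekly phase, gaps of 14, 21, 28 and 35 days mean 1, 2, 3 and 4 missed doses, so the bands largely recover such runs. This stands for weekly dosing, although 3 and 4 share a band. It fails for four-weekly dosing, where one skip (56 days) and two (84 days) both fall in >35.
- **Other summaries.** SAP 7.4.2.3 lists every CRF-reported delay or omission, computed or not. SAP 7.4.1.1 counts subjects on each drug per cycle, and SAP 8.7 names an elotuzumab dose intensity summary. These are real offsets. However, the listing does not correct the table, the per-cycle count cannot show missed weekly doses, and the visible SAP text gives no dose intensity formula.
- **Any omission.** The percentage of subjects with at least one omission is mostly unaffected. This stands, apart from the skipped C3D1.
- **Episodes.** Omission might mean an episode. The table would then have to say so, and the skipped C3D1 would still be misplaced.
- **Source of the delay count.** SAP 7.4.2.2 computes delays but describes the tabulated ones as reported. If they come from the CRF, the late-dose undercounts do not follow. This stands.
- **Visit window.** The visible text does not give the allowed window, so whether a day 6 infusion was permitted cannot be checked. Protocol 4.5.3 also expects the next cycle to start as anchored, so a long series of equally late doses is a constructed case.

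A reader might infer that doses withheld before elotuzumab is stopped are wrongly lost, since no later infusion closes the gap. The documents do not settle this. Reporting them as discontinuation is a reasonable convention, and SAP 7.4.5 summarises reasons for stopping one drug while continuing others.

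**Conclusion.** The point holds as a minor one. The gap rule does not match the anchored schedule, and followed as written it misclassifies the per-subject 1/2/3/≥4 counts. A run of k skipped doses counts as 1, a skipped Cycle 3 Day 1 becomes a delay, and an on-time dose after an early one is flagged. Most isolated skips and isolated late doses are counted correctly.

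A reader might infer that the tables simply overstate adherence, or that they are the trial's only topline measure of drug delivered. Neither follows. Undercounting is the main direction, but the early-dose and 9-days-late examples go the other way, and a dose intensity summary is planned alongside. PFS, ORR, OS, alpha and power do not depend on these tables.

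The conclusion on omissions rests on the published schedule and the SAP limits; the C3D1 result also needs the limit to follow the cycle of the current infusion. The conclusion on delays assumes that the tabulated count is the computed one. How often any of this would occur is unknown.

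**What to change.** Derive status for each planned infusion date (Cycle 1 Day 1 plus the protocol offset), using the protocol's own visit window:

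- given on time;
- given late, with days late = actual minus planned date;
- omitted, if there is no infusion in the window.

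Count planned doses in the 1/2/3/≥4 tables and keep gap length as a supplement. Count up to the date of the decision to discontinue elotuzumab where this is recorded; otherwise stop at the last infusion and report later doses as discontinuation. State whether the delay counts are computed or CRF-reported. A date-based rule also removes the double mention of Cycle 3.

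The cost is SAP wording and reprogramming of two tables. Dosing dates are already on the CRF; the discontinuation decision date is the one further input. No dosing rule changes.

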7.4.2.4 Elotuzumab Dose Interruption

The number and percentage of subjects with any interruption in their elotuzumab infusion, with 1, 2, 3, or ≥ 4 interruptions, with an interruption due to “infusion reaction”, “infusion administration issues” and “other” will be presented. In addition, duration of interruptions (in minutes) will be summarized via descriptive statistics.

A subject listing will be generated for elotuzumab IV interruptions. This listing will include reason for interruption, whether the interruption was resumed, and duration of the interruption.

7.4.2.5 Elotuzumab IV Rate Reduction

The number and percentage of subjects with any elotuzumab IV rate reduction, with 1, 2, 3, or ≥ 4 rate reductions, and with rate reductions due to “infusion reaction,” “infusion administration issues,” and “other” will be presented.

A by-subject listing will be generated for elotuzumab IV rate reductions

7.4.2.6 Pomalidomide Dose Reduction

Reduction of Pomalidomide will be computed based on the actual dose received. In any study day (excluding, cycle 1, day 1), the drug will have a calculated reduction compared to the previous day, if the actual level of the administered dose is below the actual level of the administered dose in the previous instance. The information for this analysis will be derived programmatically, using the total daily dose on the “Record of Study Medication - pomalidomide” eCRF page.

The daily dose levels are defined as follows:

- Dose level 0 or full dose (4mg)
- Dose level -1 (3mg)
- Dose level -2 (2mg)
- Dose level -3 (1mg)

The number and percentage of subjects with a dose reduction, and the lowest dose level achieved per subject (-1, -2, -3), will be presented by treatment group.

The reason for dose reduction as reported by the investigator will be tabulated for all instances with a calculated reduction based on the dose modification for Pomalidomide page. A category “unknown” will be defined for all calculated reductions with no reason reported by the investigator.

A by-subject listing of dose reductions will be generated. This will include all reported reductions per investigator, regardless of whether it met the requirements for a calculated reduction.

7.4.2.7 Pomalidomide Dose Interruption

In any cycle, the Pomalidomide dose will be considered as interrupted if there is a gap of two or more days between two dosing dates within that cycle where the patient did not receive the study drug. This will be calculated based on the information from the dose modification CRF for Pomalidomide.

The number and percentage of subjects with dose interruption, with 1, 2, 3, or ≥ 4 reported interruptions will be presented. For subjects with a computed interruption, their reason for interruption will be summarized from the dose modification CRF. For subjects without an available reason for interruption, the category “unknown” will be used.

7.4.2.8 Dexamethasone (IV) and Oral

Doses of Dexamethasone IV and oral will be categorized according to the following dose-levels

Dose Level	Reducing Dexamethasone on Weeks with Elotuzumab		Reducing Dexamethasone on Weeks Without Elotuzumab	
	PO	IV	PO	IV
0	≤ 75 years old - 28 mg	8 mg	≤ 75 years old - 40 mg	N/A
	> 75 years old - 8 mg		> 75 years old - 20 mg	
-1	≤ 75 years old - 12 mg	8 mg	≤ 75 years old - 20 mg	N/A
	> 75 years old - 2 mg		> 75 years old - 12 mg	
-2	≤ 75 years old - 0 mg	8 mg	≤ 75 years old - 12 mg	N/A
	> 75 years old - 0 mg		> 75 years old - 8 mg	
-3	≤ 75 years old - 0 mg	Contact Medical Monitor	≤ 75 years old - 0 mg	N/A
	> 75 years old - 0 mg		> 75 years old - 0 mg	

[figure not shown]
For IV dexamethasone the following summaries will be provided:

[figure not shown]
- The number of subjects with any dose delay, with 1, 2, 3, or ≥ 4 reported delays, and with a reason for delay of “hematologic toxicity”, “non-hematologic toxicity”, “AE”, “dosing error” and “other”.
- The number of subjects with any reported dose omission, with 1, 2, 3, or ≥ 4 reported omissions, and with a reported reason for omission of “hematologic toxicity”, “non-hematologic toxicity”, “AE”, “dosing error” and “other”.
- The number of subjects with any reduction in the dose of the drug, and with a reason for the reduction of “hematologic toxicity”, “non-hematologic toxicity”, “AE”, “dosing error”, and “other”).

For PO dexamethasone the following summaries will be produced:

- The number of subjects with any dose modification, and with a reason for the modification of “hematologic toxicity”, “non-hematologic toxicity”, “AE”, “dosing error” and “other”).
- The total number of modifications of the drug experienced by a subject, both overall and by the reason for the modification.

By subject listings of record of study medication for each of IV dexamethasone and PO dexamethasone will be provided.

7.4.3 Premedication Other than Dexamethasone for Hypersensitivity Reactions

A by-subject listing of pre-medication for elotuzumab, other than dexamethasone, will be provided. This listing will be generated from the “Pre-medication for elotuzumab” eCRF module and pre-medications will be coded using the BMS WHO drug dictionary.

7.4.4 Concomitant Medication

Concomitant medications are medications, other than study medication or pre-medications for elotuzumab recorded on the “Pre-medication for elotuzumab” eCRF page, which are taken by subjects any time on-study, no earlier than the first day of study drug and no later than 60 days after the last dose of study drug. Concomitant medications will be coded using the BMS WHO drug dictionary. If there is clear evidence to suggest that the medication stopped prior to the first dose of study medication, the medication will be assumed to be Prior only.

The number and percentage of subjects taking any concomitant medication and each medication (Anatomical Therapeutic Chemical [ATC] classification system drug name) will be summarized, overall and by treatment group.

A by subject listing of concomitant medication will be provided.

7.4.5 Discontinuation of Study Therapy

The number and percentage of subjects who have discontinued all study treatment and reason for discontinuation will be summarized by treatment group and overall using the subject status eCRF page from end of treatment. This summary, unlike other analyses of exposure, will include all randomized subjects and will be grouped by treatment group as randomized. This is done in order to give a full accounting of all subjects who are off study treatment, including those who were randomized but never treated.

In addition, for subjects in the Elotuzumab arm, who discontinued one drug, while continuing at least one of the other two study drugs, their reason for treatment discontinuation will be summarized based on the dose modification CRF. Subjects will be counted in this summary if there is evidence from the dosing CRF that the subject received the combination therapy in at least one cycle, followed by additional cycles, where one of the drugs in the combination was discontinued.

7.4.6 Subsequent Anti-Myeloma Therapy

The number and percentage of subjects with any subsequent systemic anti-myeloma therapy, reason for first subsequent systemic anti-myeloma therapy regimen (Documented progression of disease, Clinical deterioration without documented progression, Maintenance therapy without disease progression or clinical deterioration, or Other) and all subsequent systemic anti-myeloma therapy agents given categorized using the BMS WHO drug dictionary will be presented by treatment group.

The number and percentage of subjects with any subsequent surgery, type of first subsequent surgery (Kyphoplasty, Orthopedic surgery, Debulking surgery or Other) will be presented by treatment group.

The number and percentage of subjects with any subsequent radiation therapy will be presented by treatment group.

A by-subject listing of all subsequent surgery, all subsequent radiation therapy, and all subsequent systemic anti-myeloma therapy will be provided.

7.5 Efficacy

Efficacy analyses (PFS, ORR and OS) will be conducted on the population of all randomized subjects, grouped by arm assigned at randomization, unless otherwise noted.

Unless stated otherwise, whenever a stratified analysis is specified, the stratifications factors will be those used in the randomization (per IVRS), that is:

- Number of prior lines of therapy (2-3 vs. ≥ 4)
- ISS Staging at study entry (I-II vs. III)

The final analysis of PFS will occur after at least 71 progression events have been observed. This analyses will serve as the basis for the clinical study report. The final analysis of OS will be conducted after at least 78 deaths have been observed.

All p-values reported will be 2-sided. The alpha (α) level used for the two-sided CI will be same as nominal significance level for hypothesis testing ($\alpha = 0.2$). In addition two-sided 95% CI for these endpoints will also be provided. The p-values presented in the clinical study report will be rounded to the fourth decimal place. Point estimates and confidence bounds for efficacy variables will be rounded to the second decimal place.

